1.0 Background

Current protocols used in clinical practice for stress echocardiography evaluation include exercise efforts (bicycle and treadmill) and pharmacologic stimulation. The pharmacologic stress echocardiography in the US is almost exclusively performed with Dobutamine.

In clinical practice vasodilator agents for stress testing have been limited for the use of perfusion imaging with nuclear isotopes. Nuclear stress testing is more expensive, equipment heavy, less available and much less portable than echocardiography imaging systems. It also exposes patients to a significant radiation dose (1).

Stress echocardiography is known for its comparable accuracy in detection of obstructive coronary artery disease when compared with nuclear methods. In a highly quoted pooled analysis of 18 studies in 1304 patients who underwent exercise or pharmacologic stress echocardiography in conjunction with thallium or technetium- labeled radioisotope imaging, sensitivity and specificity were 80% and 86% for echocardiography. Corresponding values were 84% and 77% for myocardial perfusion imaging, respectively (2).

The main limitation of stress echocardiography has been imaging quality and the fact that segmental dysfunction recognition depends on the human eye assessment of wall thickening (3). New, validated, ultrasound imaging technology now exists to aid in the recognition of segmental systolic dysfunction in more objective ways, namely the use of speckle tracking imaging(4). This technology uses the systolic tracking of speckles to define tissue deformation of the different cardiac segments in all the dimensions of cardiac, systolic, mechanical motion. The quality of this technology for precise segmental function analysis relies on the use of higher frame rates (5); which can be defeated in the case of tachycardia. Since a certain level of tachycardia is needed for accuracy in Dobutamine stress echocardiography testing (DSE), therefore combining DSE with speckle tracking imaging would be sub optimal. Speckle tracking imaging values in its longitudinal dimension has also proven more reliable for all-cause mortality prediction than more traditionally accepted measures such as Left Ventricular ejection fraction (LVEF) and wall motion score index (WMSI) (6).

The use of vasodilatation for stress echocardiography examination has been performed successfully in the past, also with the use of regadenoson, but for the

**Proprietary Information of MD Anderson  

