## Proprietary Information of MD Anderson 04-13-2021

guidelines as well as financial limitations. Currently, only those who are SPECT positive may potentially receive an angiogram. We expect 210 (70%) of the 300 patients will be SPECT positive. Out of those 210 patients, 178 (85%) will actually undergo an angiography (Grp 1).

Since not all of the 300 patients will receive an angiogram, we will not be able to demonstrate directly the non-inferiority of ReSTE with regard to its accuracy of identifying ischemia when compared to SPECT imaging. However if ReSTE is truly as accurate as SPECT in its ability of identifying ischemia, then among those who are SPECT positive and also undergo an angiogram test, we expect minimum discordance between the angiogram and the ReSTE. Therefore, we aim at demonstrating that the angiogram and the ReSTE are equivalent in classifying ischemia among the SPECT positive patients; this corresponds to test if ReSTE is as accurate as SPECT in the diagnosis of ischemia at least among SPECT positive patients. Assuming that the true respective ischemia rates diagnosed by angiogram and ReSTE are  $P_0$  and  $P_1$ , we will perform equivalence test to test the following hypotheses:

$$H_0: |P_1 - P_0| > 0.05;$$

$$H_1: |P_1 - P_0| \leq 0.05;$$

If we observe a 7% discordance rate (equivalent to 12 of the 178 patients) between the angiogram and ReSTE results, and we were to allow a  $\pm 5\%$  tolerance limit, we would have 80% power to declare equivalence using a one-sided paired test of equivalence in proportion (alpha of 0.05), i.e. we will reject the null hypothesis that  $|P_1 - P_0| > 0.05$  and accept the alternative hypothesis that  $|P_1 - P_0| \leq 0.05$ . Lower discordance rates would yield higher power, so this estimate of power is rather conservative. The sample size calculation was performed using nQuery Advisor 7.0.

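### The 80% power belongs to one bound of a two-bound equivalence test; the planned test has about 52%, and nothing supports calling the estimate conservative

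*Combined protocol and SAP*

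**What the plan says.** Section 6.0 (Design and sample size/power) sets the alternative hypothesis that P1 (ReSTE) and P0 (angiogram) differ by no more than 0.05 in either direction, among SPECT-positive patients who have an angiogram. The analysed number is given as "Out of those 210 patients, 178 (85%) will actually undergo an angiography (Grp 1". The planning condition is "If we observe a 7% discordance rate (equivalent to 12 of the 178 patients", which is said to give "80% power to declare equivalence using a one-sided paired test of equivalence in proportion (alpha of 0.05". The paragraph ends: "Lower discordance rates would yield higher power, so this estimate of power is rather conservative". Earlier it argues that if ReSTE is truly as accurate as SPECT, then in this group "we expect minimum discordance between the angiogram and the ReSTE". The Analysis Plans name Tango's paired equivalence test as primary.

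No source is given for the 7%, and no true difference is stated. Section 1.0 reports, from a pooled analysis of exercise or pharmacologic stress studies, that "sensitivity and specificity were 80% and 86% for echocardiography" and "Corresponding values were 84% and 77% for myocardial perfusion imaging".

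**The concern.** There are two separate matters. First, the hypothesis has two bounds, so equivalence is declared only if both are cleared; a power figure for one bound overstates the chance of success. Second, angiography is the reference standard, so discordance with it is simply ReSTE's false negatives plus its false positives. A 7% total is small beside the error rates quoted in Section 1.0, and the plan offers nothing to justify calling it cautious.

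This is the only power justification for the primary objective. If the real chance of success is nearer one half or lower, a result that does not show equivalence is likely even when ReSTE performs well. It could then be misread as ReSTE being less accurate than SPECT.

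**Working it through.** **Inputs.** n = 178, margin 0.05, one-sided alpha 0.05 (z = 1.645), discordance 7% (12/178 = 6.74%), all from Section 6.0. The true difference is not stated; zero is assumed because it reproduces the plan's figure.

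**1. Reproducing the 80%.** The standard error at zero difference is sqrt(0.07/178) = 0.01983, and 0.05/0.01983 = 2.521.
- One bound: Φ(2.521 − 1.645) = Φ(0.876) = 81%. This is the plan's figure.
- Both bounds: 2 × 0.81 − 1 = 62%.

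**2. The test actually planned.** Power was computed by enumerating the discordant counts and applying Tango's score statistic at −0.05 and +0.05, each at 5%.

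| Power at 7% discordance, zero difference | One bound | Both bounds |
|---|---|---|
| Normal approximation | 81% | 62% |
| Exact, Tango test | 76% | 52% |

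At 12/178 the exact two-bound figure is 55%.

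The plan's own 12 discordant patients can be checked by hand. Let b be false positives, c false negatives and d = −0.05. The statistic is (b − c − nd)/sqrt{n[2q + d(1 − d)]}, where q is the larger root of 2n·q² + [−b − c + (2n − b + c)d]q − c·d(1 − d) = 0.
- Split 5/7: q = 0.0690, statistic = 6.9/3.90 = 1.77. Passes.
- Split 4/8: q = 0.0665, statistic = 4.9/3.79 = 1.29. Fails.

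So only 5/7, 6/6 and 7/5 declare equivalence. With exactly 12 discordant patients and equal chances of either direction, that has probability (792 + 924 + 792)/4096 = 61%. Variation in the number of discordant patients brings it down to the 55% above.

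**3. Exact two-bound power at zero difference**

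| Discordance | 4% | 7% | 10% | 12% | 15% | 17% |
|---|---|---|---|---|---|---|
| Power | 80% | 52% | 28% | 16% | 6% | 2% |

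**4. Is 7% cautious?** The plan gives no angiogram-positive share π for Grp 1, so I assume 50% to 92.5%. The upper end follows from the plan's 70% SPECT positivity with 84%/77%: prevalence = (0.70 − 0.23)/(0.84 − 0.23) = 77.0%, and PPV = 0.84 × 0.770/0.70 = 92.5%. I also assume that those who have an angiogram are a random subset of SPECT positives.

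*Echo at 80%/86%, errors independent of SPECT given disease.* Discordance = 0.20π + 0.14(1 − π); P1 − P0 = 0.14(1 − π) − 0.20π = 0.14 − 0.34π.
- π = 50%: discordance 17.0%, difference −3.0 points.
- π = 92.5%: discordance 0.185 + 0.0105 = 19.6%, difference −17.4 points.
- The difference passes −5 points once π exceeds 0.19/0.34 = 56%. The chance of declaring equivalence is at most 1.7%.

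*Echo at 80%/86%, misses maximally shared with SPECT, false positives independent.* The miss rate among diseased SPECT positives is (20 − 16)/84 = 4.76%. Discordance = 0.0476π + 0.14(1 − π).
- π = 50%: 2.4% + 7.0% = 9.4%, difference +4.6 points, power 6%.
- π = 75%: 3.57% + 3.50% = 7.07%, difference about zero, power 52%.
- π = 89.5%: 5.7%, difference −2.8 points, power 29%.

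Over the assumed range, discordance is about 5.5-9.4% and power about 6-52%.

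*ReSTE given SPECT's own 84%/77%.*
- Independent errors: discordance 16.5-19.5%, chance of declaring equivalence at most 0.9%.
- Every diseased SPECT-positive patient detected, false positives independent: at π = 92.5%, discordance is 0.23 × 0.075 = 1.7% and power about 80%; at π = 95% it is 94%.
- ReSTE agreeing with SPECT in every patient: discordance = 1 − PPV = 7.5%, all in one direction, and equivalence is declared 0.2% of the time.

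**The case against.** The strongest defence is that the 7% is not refuted. With 80%/86%, fully shared misses and 75% of Grp 1 angiogram-positive, discordance is 7.07% with essentially no net difference, which is the plan's own planning point. The 80%/86% are also not ReSTE figures: they come from conventional stress echo, whose reliance on visual reading Section 1.0 says speckle tracking is meant to improve. Both points stand. A reader might infer that the protocol's accuracy figures contradict the 7%; the documents support only that it is unsourced and looks optimistic.

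Three further points stand. Lower discordance does raise power when the true difference is held at zero. In most of the independent-error cases the true difference lies outside 5 points, so failing to declare equivalence is the correct outcome there and not low power. And a reader might infer that no dependence between the tests can give 80% power, or that a ReSTE as accurate as SPECT is almost bound to fail. The 84%/77% case with full co-detection and a high angiogram-positive share shows that neither holds in general.

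One could also argue that the word one-sided shows a single bound was intended. The hypotheses, however, are written on the absolute difference, and the objective is equivalence. Two one-sided tests at 5% fit that wording, but power must then be the chance of passing both. None of these points touches the gap between 80% and 52%, which arises at the plan's own inputs.

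**Conclusion.** The power statement is wrong as written. At the plan's own 7% discordance, 178 patients and zero difference, the two-bound Tango test has about 52% power (62% by normal approximation), not 80%. This rests only on the plan's inputs and the unstated but favourable assumption of zero difference. The shortfall at 7% comes from counting one bound and from using a normal approximation; it does not come from the discordance assumption.

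Separately, the claim of conservatism is unsupported. Under the assumed 50-92.5% angiogram-positive share and 80%/86% accuracy, discordance runs from about 5.5-9.4% with misses maximally shared to 17-20% with independent errors. This part depends on borrowed accuracy figures and an assumed dependence, so it shows that 7% lies towards the optimistic end, not that it is impossible.

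The inference from equal accuracy to minimal discordance also does not hold in general: a ReSTE that copied SPECT exactly could fail the primary test. Failure to show equivalence therefore does not by itself show that ReSTE is less accurate than SPECT.

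**What to change.** In Section 6.0 (Design and sample size/power):

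- Replace the 80% with the two-bound power of the planned Tango test, about 52% at 7% discordance and zero difference, and state the assumed true difference.
- Add a table of that power over about 4-20% discordance, with zero and non-zero values of P1 − P0.
- Delete the clause calling the estimate conservative, and the inference that equal accuracy implies minimal discordance with the angiogram.
- State that failure to show equivalence will not be read as ReSTE being less accurate than SPECT.

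The cost is rewording and one table, with no extra patients and no change to the test. The price is a less favourable power statement. For scale, 80% two-bound power at 7% would need 0.07 × [(1.645 + 1.282)/0.05]² = about 240 angiograms by normal approximation, more than the 210 SPECT-positive patients expected.

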### Analysis Plans

Patients' demographic and clinical characteristics will be summarized using descriptive statistics such as mean, standard deviation, median, interquartile range (IQR), frequency where appropriate. We will apply Student t-test/Wilcoxon test and Kruskal-Wallis test/ANOVA to compare continuous variables, and the chi-square test or the Fisher's exact test (14) to compare categorical variables in different patient groups (Grp 1).

As the primary analysis, we will use a paired test of equivalence for proportions proposed by Tango (11) to test the equivalence of the two ischemia tests among the SPECT positive patients.

Among the SPECT positive patients, Standard measures of clinical performance of ReSTE including sensitivity, specificity and positive and negative predictive values (12) will be estimated first. Additionally, the corresponding 2-sided 95% CI of binomial proportion will be calculated. We will use Receiver operating

characteristic (ROC) curve analysis (13) to assess the best cut-off for the ReSTE test, and calculate the area under the ROC curve to assess the performance of different cut-offs of ReSTE for the group.

For the secondary endpoints including cardiac event rates at Day 30 post-operation, we will provide estimates along with 95% confidence intervals (Grp 2). Univariate and multivariate logistic regression models will be fit to identify risk factors associated with the Day 30 events. Specifically, we will assess whether or not ReSTE adds predictive information above and beyond SPECT in predicting the Day 30 events. We hypothesize that patients who are positive on both SPECT and ReSTE have the highest Day 30 cardiac complication rates while those who are negative on both tests have the lowest cardiac complication rates. We will test whether the difference in statistical predictive accuracy between different logistic regression models (with or without ReSTE in the models) is significant (14). The predictive accuracy of the various logistic regression models will be quantified by C statistic, which provides the area under the receiver operating characteristics curve (13,14). To protect against over-fitting in the stepwise regression, we will use a bootstrap procedure to obtain an unbiased estimate of the C-index. These analyses will be performed using all patients for whom we have available data.

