**Proprietary Information of MD Anderson**  
**04-13-2021**

echocardiography (ReSTE) are equivalent in classifying ischemia among SPECT positive patients; this corresponds to test if ReSTE is as accurate as SPECT in the diagnosis of ischemia at least among SPECT positive patients (Grp 1).

Secondary aims: assess whether or not ReSTE adds predictive information above and beyond SPECT in predicting 30d post-operative cardiac events (Grp 2).

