### 4.0 Research Plan and Methods

**Study Outline:**

Upon signed informed consent and enrollment, patients will be imaged during regadenoson infusion using the stated imaging protocol. If two contiguous segments in any of the apical views are not visible patients will not be registered in the study and will be entered in CoRE as screen failures due to eligibility criteria.

For ECHO, images will be stored for strain analysis in the ECHO PAC system and will be analyzed by a single blinded investigator ([name]). All strain will be obtained using the 2D strain analysis pathway. Global longitudinal strain (GLS), 2D LVEF with bi-plane Simpsons method of calculation, end diastolic volume (EDV bi-plane), end systolic volume (ESV bi-plane) and stroke volume (SV) values will be obtained and saved.

SPECT images will be interpreted by a blinded pool of faculty that includes radiologists and cardiologists from the institution. On those patients (Grp 2) who are studied pre-operatively the proposed surgery description and total surgical time will be recorded. Immediate post-op cardiac events (MACE) and 30 day post-operative cardiac events (MACE) will be recorded from inpatient records by chart review or if needed by telephone contact to patients. The post-operative events will be used to report prognostic accuracy of both testing methods and for comparison.

Patients who have coronary angiography or coronary CT angiograms will have the imaging data and test report data saved and stored for the final analysis (Grp 1).

The accuracy of both tests will be compared in those patients with angiogram data (Grp 1).

**Study Design:** Prospective comparison for demonstration of equivalence. Will attempt to show same specificity and sensitivity with ReSTE compared to SPECT at detecting (segmental/coronary) distribution defects.

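### Added value of ReSTE over SPECT rests on an unnamed test of a C-statistic difference; a designated likelihood-ratio test of the ReSTE term would answer the secondary aim directly

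*Combined protocol and SAP*

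**What the plan says.** Section 2.0 makes the added predictive value of ReSTE over SPECT for 30-day post-operative cardiac events the secondary aim, in Grp 2. Section 6.0, Analysis Plans, repeats it: "Specifically, we will assess whether or not ReSTE adds predictive information above and beyond SPECT in predicting the Day 30 events".

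The only inferential step stated for that aim is: "We will test whether the difference in statistical predictive accuracy between different logistic regression models (with or without ReSTE in the models) is significant". That sentence closes with a citation to reference 14, a general text on regression modelling that the same section also cites for Fisher's exact test. The following sentence reads: "The predictive accuracy of the various logistic regression models will be quantified by C statistic".

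Three other statements bear on the point:
- "Univariate and multivariate logistic regression models will be fit to identify risk factors associated with the Day 30 events". No covariates are listed.
- "To protect against over-fitting in the stepwise regression, we will use a bootstrap procedure to obtain an unbiased estimate of the C-index". The bootstrap is there to estimate the C-index, not to test a difference.
- Section 4.0, Study Outline: "The post-operative events will be used to report prognostic accuracy of both testing methods and for comparison". No method is given there.

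The document does not name a test for the C difference, designate a test of the ReSTE coefficient, or state that SPECT is kept in both models. It gives no Grp 2 size, event rate, effect size, alpha or power for this aim.

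**The concern.** Whether ReSTE adds information beyond SPECT is a question about the ReSTE term in a model that already contains SPECT. A likelihood-ratio test (LRT) of that term answers it directly. A test of the change in C is indirect: the C statistic depends only on ranks, and it moves little once the base model already discriminates.

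There is also a calibration problem. When ReSTE adds nothing, the two fitted models rank patients almost identically. The usual standard error for a difference between two C statistics treats the fitted scores as if they were fixed, and the normal approximation then fails. DeLong's test, applied this way with covariates present, rejects far less often than its nominal 5%, and power falls with it.

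At stake is the secondary aim: a real independent contribution of ReSTE could be missed more often than it need be. Because the plan leaves the test open, the choice between a coefficient p-value and a C-difference p-value could also be made after the data are seen.

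**Working it through.** **No plan figure to reproduce.** The only power statement in the document (80%) belongs to the primary equivalence test and does not bear on this aim. The check is therefore a simulation.

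**Inputs.** From the document: "We expect 210 (70%) of the 300 patients will be SPECT positive". This is stated for all enrolled patients, not for Grp 2, so using it for Grp 2 is an assumption. All other inputs are assumed:
- Grp 2 size and event rate: 200 at 10% (200 x 0.10 = 20 events); 300 at 15% (300 x 0.15 = 45); 150 at 5% (150 x 0.05 = 7.5).
- ReSTE positive in 60% of SPECT-positive and 20% of SPECT-negative patients.
- SPECT odds ratio 2; ReSTE odds ratio 1 (null) or 2.5.
- Base model: SPECT alone, SPECT plus one moderate covariate (log odds ratio 0.5 per SD), or SPECT plus three (0.4 each).

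**Tests, two-sided 5%.**
- LRT: 2(l1 - l0) against chi-square on 1 df, where l1 and l0 are the log-likelihoods with and without ReSTE.
- DeLong: (C1 - C0)/SE against 1.96, using the in-sample C statistics.

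**Power at ReSTE odds ratio 2.5** (2,000 datasets per cell; Monte Carlo SE up to sqrt(0.42 x 0.58 / 2000) = 1.1 points):

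| Base model | Events | LRT | DeLong |
|---|---|---|---|
| SPECT alone | about 20 | 43% | 35% |
| + one moderate covariate | about 20 | 42% | 10% |
| + three moderate covariates | about 20 | 41% | 7% |
| SPECT alone | about 45 | 74% | 68% |
| + one moderate covariate | about 45 | 72% | 18% |
| + three moderate covariates | about 45 | 70% | 13% |

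Repeat runs agree within simulation error. Together they give 41-43% versus 7-10%, and 70-73% versus 13-20%.

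**Rejection under the null, covariates in the model.** DeLong 0.2-0.5%; LRT 4.6-5.3%.

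**Mechanism.** A second set of runs, with a latent correlation of 0.5 between SPECT and ReSTE, shows it at about 45 events. With SPECT alone, mean C rises from 0.586 to 0.645, a gain of 0.059. With three covariates it rises from 0.737 to 0.762, a gain of 0.025. LRT power is the same in both (66%), while DeLong power falls from 57% to 13%.

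**Other ways of testing the C difference, covariates in the model** (ReSTE odds ratios 2.5 and 3.5). The ratio of LRT power to the power of each test is:
- bootstrap percentile interval shifted for optimism: 1.2 to 2.4;
- other bootstrap versions: 1.5 to 4.4 in the first set of runs, up to 5.3 in the second;
- C difference with its critical value taken from null simulation: 1.06 to 1.8.

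Not every version is conservative. With SPECT alone, an uncorrected percentile bootstrap rejects in 14-25% of null datasets.

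**Very few events (about 7-8).** With covariates, LRT 21-23% versus DeLong 9-13%, with LRT null rejection of 6.3-7.6%. With SPECT alone there is no gain (23% versus 24%).

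**The case against.** The strongest reply is that the comparator is not the plan's. The document never mentions DeLong, and the one C-related procedure it names is a bootstrap, against which the gain is smaller. Against a C test calibrated under the null the gain is modest. This stands, and it is why no single power multiple should be attached to the plan. It does not remove the point, because the result depends on which test is used and the plan names none.

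Second, the plainest reading of the aim is SPECT versus SPECT plus ReSTE, where the tests perform about equally. This also stands. The large differences need covariates in the comparison; the plan foresees multivariate models but does not say which terms enter this one.

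Third, the sentence describes models with and without ReSTE and cites a regression text, so a nested-model test may have been intended. The content of that reference cannot be checked from the documents. The citation does not identify a test, and the next sentence points to the C statistic. A ReSTE coefficient would be available from the multivariate models, but it is not designated as the test of the aim.

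A reader might also infer that stepwise selection could drop SPECT, leaving a result not adjusted for it. The documents do not support that as a finding. They mention stepwise regression without saying that it applies to this comparison, and the wording of the aim implies that SPECT stays in. The most that can be said is that the plan should state this explicitly.

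**Conclusion.** The point holds as a cheap improvement to the secondary analysis. The only stated test of added value is a significance test of a difference in C, with no procedure named, while a better-matched test is available from the same models.

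The size is illustrative. Grp 2 size, event rate, odds ratios and covariates are all assumed. The 45-event case is generous: it puts all 300 enrolled patients in Grp 2, although Section 3.0 also admits patients evaluated for symptoms. What does not depend on the exact inputs is the pattern across the covariate settings tried at about 20 to 45 events: DeLong rejected in under 1% of null datasets, and the LRT had more power than each C-difference test examined.

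A reader might infer that the plan as written gives up a several-fold amount of power. The documents do not support that. It would be true only if a DeLong-type test were used with covariates in the model, and neither is specified. Nor does the LRT rescue a small study: about 41-43% power at odds ratio 2.5 with about 20 events is still low. The primary equivalence analysis is untouched.

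**What to change.** In Section 6.0, Analysis Plans:

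1. State that added value is tested by a 1-df likelihood-ratio test of ReSTE in a fixed logistic model, with SPECT, and any short pre-named covariate list, in both models.
2. State that no stepwise selection is used for this comparison. Keep stepwise modelling as exploratory risk-factor work.
3. Report the bootstrap-corrected C statistics of both models and their difference with an interval, as description.
4. Add that a non-significant result is not evidence of no added value.

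The cost is wording only; data and software are unchanged. There are two downsides. Covariates must be fixed in advance, and the LRT is slightly liberal with very few events, so the covariate list should be short.
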